3. AEs and concomitant therapies will be recorded throughout the trial, but will be specifically asked for at the time points indicated in the Flow Chart above.

Proprietary confidential information © 2017 Boehringer Ingelheim International GmbH or one or more of its affiliated companies

4. Pre-medication of rabeprazole will be started at the following day of Day 3 of Visit 2.
5. Rabeprazole will be administrated 4 hour prior to administration of DE on Day 1 of Visit 3
6. Inserting the pH sensor to be completed within approximately 3 hours prior to DE administration. Intragastric pH will be checked at predose, 15, 30 minutes, 1, 2 hours after drug administration of DE. The pH sensor is removed after collecting gastric pH at 2 hours after DE administration. Data will be collected and entered in the electric case report form.
7. The time is approximate; the procedure is to be performed and completed within 3 hours prior to DE administration.
8. Genotyping of cytochrome P450 2C19 (CYP2C19) is mandatory. Pharmacogenomics sample will be taken together with the pharmacokinetics sample at 1 hour after administration of DE on Day 1 of Visit 2, but can be taken at subsequent visit.
9. If several actions are indicated at the same time point, the intake of meals or water will be the last action.
10. In case of premature discontinuation, 5-14 days after the last DE administration
11. End of trial examination includes physical examination, body weight, vital signs, ECG, safety laboratory, recording of AEs and concomitant therapies.

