### **3.3.4 Removal of subjects from therapy or assessments**

#### **3.3.4.1 Removal of individual subjects**

An individual subject is to be removed from the trial if:

1. The subject withdraws consent for trial treatment or trial participation, without the need to justify the decision
2. The subject needs to take concomitant drugs that interfere with the investigational product or other trial medication

Proprietary confidential information © 2017 Boehringer Ingelheim International GmbH or one or more of its affiliated companies

3. The subject is no longer able to participate for other medical reasons (such as surgery, AEs, or diseases)
4. An AE or clinically significant laboratory change or abnormality occurred that is considered by the investigator to warrant discontinuation of treatment.
5. Clinical evidence of prolongation of coagulation, i.e., prolonged bleeding at the venipuncture site (defined as >15-minute compression necessary)
6. Sustained minor bleedings which cannot be controlled by local haemostasis, or any other bleeding event considered clinically relevant by the investigator.

A subject can also be removed from the trial if eligibility criteria are being violated or if the subject fails to comply with the protocol (for instance, by non-adherence to dietary rules, or non-attendance at study assessments).

If a subject is removed from or withdraws from the trial prior to first administration of trial medication, the data of this subject will not be entered in the case report form (CRF) or trial database and will not be reported in the clinical trial report (CTR). If a subject is removed from or withdraws from the trial after first administration of trial medication, this will be documented and the reason for discontinuation must be recorded in the CRF. In this case, the data will be included in the CRF/trial database and will be reported in the CTR. At the time of discontinuation a complete end of trial examination will be performed if possible and the information will be recorded in the CRFs. If the discontinuation occurs before the end of the residual effect period (REP) (see [Section 5.2.2.2](#)), the discontinued subject should if possible be questioned for AEs and concomitant therapies at or after the end of the REP in order to ascertain collection of AEs and concomitant therapies throughout the REP, if not contrary to any consent withdrawal of the subject. These discontinuations will be discussed in the CTR.

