#### 5.2.2.2 Adverse event collection and reporting

##### **AEs collection**

Upon enrolment into a trial, the subject's baseline condition is assessed (for instance, by documentation of medical history/concomitant diagnoses), and relevant changes from baseline are noted subsequently.

[figure not shown]
Subjects will be required to report spontaneously any AEs as well as the time of onset, end, and intensity of these events. In addition, each subject will be regularly assessed by the medical staff throughout the clinical trial and whenever the investigator deems necessary. As a minimum, subjects will be questioned for AEs (and concomitant therapies) at the time points indicated in the [Flow Chart](#). Assessment will be made using non-specific questions such as 'How do you feel?'. Specific questions will be asked wherever necessary in order to more precisely describe an AE.

A careful written record of all AEs shall be kept by the investigator in charge of the trial. Records of AEs shall include data on the time of onset, end time, and intensity of the event as well as any treatment or action required for the event and its outcome.

The following must be collected and documented on the appropriate CRF(s) by the investigator:

- From signing the informed consent onwards through the residual effect period (REP), until an individual subject's end of trial:
  - All AEs (serious and non-serious).
  - The only exception to this rule are AEs (serious and non-serious) in Phase I trials in healthy volunteers, when subjects discontinue from the trial due to screening failures prior to administration of any trial medication. In these cases, the subjects' data must be collected at trial site but will not be entered in the CRF or trial database and will not be reported in the CTR.
- After the individual subject's end of trial:
  - The investigator does not need to actively monitor the subject for AEs but should only report relevant SAEs which [REDACTED] may become aware of.

Proprietary confidential information © 2017 Boehringer Ingelheim International GmbH or one or more of its affiliated companies

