The REP for DE, when measurable drug levels effects are still likely to be present, is defined as 3 days after the last administration of DE. Therefore, all AEs which occurred through the treatment phase and throughout the REP will be considered as on treatment; please see [Section 7.3.3](#). Events which occurred after the REP will be considered as post treatment events.

The follow-up period describes the period of time from the last administration of trial medication including the REP until the end of trial examination (last per protocol contact).

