### **6.2.3      End of trial and follow-up period**

For AE assessment, laboratory tests, recording of ECG and vital signs, and physical examination during the end of trial period, see [Sections 5.2.2](#) to [5.2.5](#).

Subjects who discontinue treatment before the end of the planned treatment period should visit the trial site undergo the examination to check the subject's safety where applicable, and then undergo the EOT examination 5 to 14 days after the day of last treatment.

All abnormal values (including laboratory parameters) that are judged clinically relevant by the investigator will be monitored using the appropriate tests until a return to a medically acceptable level is achieved. (S)AEs persisting after subject's end of trial must be followed up until they have resolved, have been sufficiently characterised, or no further information can be obtained.

The end of the trial as a whole is defined by the 'last regular visit completed by last subject' or 'end date of the last open AE' or 'date of the last follow-up test' or 'date of an AE has been decided as sufficiently followed-up', whichever is latest.

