7.8.1 Adverse events

AEs will be coded with the most recent version of MedDRA. The analyses of AEs will be descriptive in nature. All analyses of AEs will be based on the number of subjects with AEs and not on the number of AEs.

For analysis of AE attributes such as duration, severity, etc. multiple AE occurrence data on the CRF, will be collapsed into AE episodes provided that all of the following applies:

- The same MedDRA lowest level term was reported for the occurrences
- The occurrences were time-overlapping or time-adjacent (time-adjacency of 2 occurrences is given if the second occurrence started on the same day or on the day after the end of the first occurrence)
- Treatment did not change between the onset of the occurrences OR treatment changed between the onset of the occurrences, but no deterioration was observed for the later occurrence

For further details on summarisation of AE data, please refer to ([5](#), [6](#)).

The residual effect period (REP) for Dabigatran etexilate (DE) is defined as 3 days after the last administration of DE. Therefore, all AEs which occurred through the treatment phase and throughout the REP are considered as treatment emergent.

The analysis of AEs will be based on the concept of treatment emergent AE. That means that all AEs occurring between the first intakes of dabigatran till 3 days after will be assigned to treatment “dabigatran” (or “reference”) in period 1. In period 2 all AEs occurring between the first intake of rabeprazole until before the intake of dabigatran will be assigned to “rabeprazole“, then after the intake of dabigatran until 3 days later to “dabigatran+ rabeprazole” or “test”. AEs occurring after “dabigatran” but after the REP in period 1 will be assigned to ‘washout’. AEs occurring after “dabigatran+ rabeprazole” but before EOT will

be assigned to 'post-treatment'. All AEs occurring before first drug intake will be assigned to 'screening' and all AEs occurring after EOT will be assigned to 'post-study'.

According to ICH E3 (7), AEs classified as 'other significant' needs to be reported and will include those non-serious with

- (i) 'action taken = discontinuation' or 'action taken = reduced', or
- (ii) marked haematological and other lab abnormalities or lead to significant concomitant therapy as identified by the Clinical Monitor/Investigator at a RPM/database lock (DBL) meeting.

An overall summary of AEs will be presented.

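### End of trial examination after premature discontinuation is timed differently in three places, and an early one gives adverse events in the residual effect period two labels in the SAP

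*Protocol*

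**What the plan says.** **Timing of the examination**

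- Protocol 3.3.4.1: "At the time of discontinuation a complete end of trial examination will be performed if possible and the information will be recorded in the CRFs".
- Flow Chart footnote 10, attached to the EOT visit: "In case of premature discontinuation, 5-14 days after the last DE administration".
- Protocol 6.2.3: a subject who stops early comes to the site for a safety check where applicable, and should "then undergo the EOT examination 5 to 14 days after the day of last treatment".

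**AE collection and the REP**

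- Protocol 5.2.2.2: the REP "is defined as 3 days after the last administration of DE". AEs up to its end count as on treatment. Collection runs "From signing the informed consent onwards through the residual effect period (REP), until an individual subject's end of trial". After that point active monitoring is no longer required.
- Protocol 3.3.4.1, in the REP provision that follows the examination sentence: where discontinuation falls inside the REP, "the discontinued subject should if possible be questioned for AEs and concomitant therapies at or after the end of the REP". The stated aim is that collection should cover the whole of that period. This is subject to any withdrawal of consent.

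**Labels**

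- SAP 7.8.1 assigns AEs from DE intake until 3 days later to 'dabigatran' in Period 1, and to 'dabigatran + rabeprazole' after the second DE dose. It also says that "all AEs occurring after EOT will be assigned to 'post-study".
- SAP Table 6.1.1 starts the 'post-study' interval at 0:00 on the day after EOT.
- The AE frequency table in SAP 7.8.1 covers 'dabigatran', 'rabeprazole' and 'dabigatran + rabeprazole' only.

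**The concern.** Under 3.3.4.1 the examination can fall one day after DE. Under footnote 10 and 6.2.3 it falls at least five days after. Both passages give it the same name, and Protocol 5.2.2.2 describes the end of trial examination as the final contact under the protocol. A site that performs an examination at discontinuation and another later has no text telling it which date is the EOT date.

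That date drives the SAP. If the early examination is recorded as EOT, the 'post-study' label can begin while the REP is still running. The subjects concerned include those removed for bleeding or for prolonged bleeding at the venipuncture site (3.3.4.1, removal criteria 5 and 6). What is at stake is whether a later AE in such a subject is counted against the treatment that he received, and whether two programmers working from the same SAP would produce the same table.

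**Working it through.** There is no planned figure to reproduce. The check sets the passages on one timeline.

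**Inputs.** DE is given at 10:00 on Day 1 and rabeprazole at 06:00 (Flow Chart). Pre-medication starts the day after Day 3 of Visit 2, and its first dose is 100 h before the second DE dose (Flow Chart and footnote 4). The REP is 3 days = 72 h (Protocol 5.2.2.2). The EOT window is 5 to 14 days (footnote 10, 6.2.3). 'Post-study' starts at 0:00 on EOT + 1 day (SAP Table 6.1.1).

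**Step 1: early examination against the REP.** Assume that the examination at discontinuation is recorded as EOT. The start of 'post-study' is the time from 10:00 on Day 1 to 0:00 on the day after EOT. The overlap is 72 h minus that start.

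| EOT recorded on | 'Post-study' starts, h after DE | Overlap with REP |
|---|---|---|
| Day 1 | 14 | 72 − 14 = 58 h |
| Day 2 | 14 + 24 = 38 | 72 − 38 = 34 h |
| Day 3 | 38 + 24 = 62 | 72 − 62 = 10 h |
| Day 4 | 62 + 24 = 86 | none |

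Read literally, SAP 7.8.1 applies the label from EOT itself. For an examination at 24 h the overlap is then 72 − 24 = 48 h. The arithmetic is the same after the second DE dose, with 'dabigatran + rabeprazole' as the competing label.

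**Step 2: later examination against the REP.** The 5 to 14 day window opens at 5 × 24 = 120 h, after the REP ends at 72 h. No overlap arises if the later visit is the EOT. The double label therefore depends entirely on the status of the early examination, which the documents leave open.

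**Step 3: footnote 10 against 6.2.3.** If DE was the last drug taken, the two windows coincide. They can differ only when the last dose was rabeprazole pre-medication. The first such dose is 72 − 4 = 68 h after the first DE dose, and the second DE dose is at 68 + 100 = 168 h = 7 days. The four pre-medication doses therefore fall on calendar days 3, 4, 5 and 6 after the first DE dose. If 'treatment' includes rabeprazole, the window in 6.2.3, counted from the last DE, is:

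| Last rabeprazole dose, days after DE | 6.2.3 window | Footnote 10 window | Days in both |
|---|---|---|---|
| 3 | 8 to 17 | 5 to 14 | 8 to 14 |
| 4 | 9 to 18 | 5 to 14 | 9 to 14 |
| 5 | 10 to 19 | 5 to 14 | 10 to 14 |
| 6 (Day −1 of Visit 3) | 6 + 5 = 11 to 6 + 14 = 20 | 5 to 14 | 11 to 14 |

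For removal on Day −1 of Visit 3, footnote 10 is already open and allows EOT that same day, up to day 14. The wider reading of 6.2.3 requires days 11 to 20.

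Both readings of 'treatment' have textual support. The synopsis lists 5 days of rabeprazole under duration of treatment, and Table 4.1.4: 1 includes rabeprazole in the test treatment. Protocol 3.1 calls the Day −4 to −1 doses pre-medication and describes the treatments as the single DE dose with or without rabeprazole.

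**Step 4: effect of the label.** SAP 7.8.1 calls AEs in the REP treatment emergent but gives no precedence over its own 'post-study' rule. Protocol 7.3.3 likewise assigns events after the end of trial examination to 'post-study'. An event so labelled falls outside the three columns of the frequency table, although it would still appear in the AE listing.

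**The case against.** The best defence is that 6.2.3 describes two steps and 3.3.4.1 supplies the first of them. A site that does a complete examination at discontinuation and sees the subject again inside the 5 to 14 day window meets all three passages. The EOT date is then the later one, and the double label does not occur. This stands as a possible reading, so it would be wrong to infer that the passages cannot all be followed. Even on the wider meaning of 'treatment', days 11 to 14 satisfy both windows. But 3.3.4.1 calls its examination a complete end of trial examination, and no passage says that a second one follows.

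A reader might also infer that the early examination closes AE collection inside the REP. The documents do not support that. Section 3.3.4.1 itself provides questioning at or after the end of the REP for this purpose, and 5.2.2.2 runs collection through the REP. That questioning is conditional on feasibility and consent, but a condition is not closure.

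Nor can one infer that a discontinued subject may get no laboratory, ECG or vital-sign check after exposure. The EOT examination includes all three (footnote 11) and is planned after DE on every reading, although at discontinuation 3.3.4.1 asks for it only where possible. The Flow Chart also schedules them at 24 h. Sections 4.2.1, 5.2.2.2 and 6.2.3 provide for supervision, for follow-up of persisting AEs and for monitoring of relevant abnormal values.

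Finally, SAP 7.8.1 treats AEs in the REP as treatment emergent, which favours the DE label. That shows the intent, but the competing rule remains in the same section.

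**Conclusion.** The inconsistency in timing is real, and so is its consequence for labelling. The consequence is conditional. It needs a subject who discontinues within about two days of a DE dose, and a site that records the examination at discontinuation as EOT. For EOT on Day 2, events from 38 h to 72 h after DE (34 h) carry two labels. The range is 10 to 58 h for EOT on Days 3 to 1. The gap between footnote 10 and 6.2.3 rests on counting rabeprazole pre-medication as treatment.

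Severity is low. The documents give no expected number of discontinuations. Only discontinued subjects among the 36 planned are affected, the safety analysis is descriptive, and the primary pharmacokinetic endpoints are not touched. One subject moved out of a treatment column changes that row by 1/36 = 2.8 percentage points if all 36 are treated. In the earlier single-dose 110 mg tablet study described in Protocol 1.2, 35 subjects had two AEs and no bleeding, so few such events are likely.

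**What to change.** **Protocol.** Reconcile 3.3.4.1, Flow Chart footnote 10 and 6.2.3 into one rule. It should name the anchor dose (DE, rabeprazole, or the later of the two) and say whether the examination at discontinuation is the EOT or a separate check. Which timing applies is for the sponsor and the investigator; this review does not propose one.

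**SAP Table 6.1.1 and 7.8.1.** Start 'post-study' at the later of 0:00 on EOT + 1 day and the end of the REP, so that no AE within the REP is labelled 'post-study'. This applies the definition already given in Protocol 5.2.2.2. It changes nothing for subjects whose EOT falls in the 5 to 14 day window, because that window opens at 120 h. The SAP abbreviation list should also agree with the protocol's: it expands EOT as end of treatment, where the protocol has end of trial.

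**Cost.** Wording in both documents and one derivation rule in the AE programs. Depending on the rule chosen, there is at most one return visit for a discontinued subject, which 6.2.3 already foresees. Sample size and the primary analysis are unchanged.

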#### **3.3.4.2 Discontinuation of the trial by the sponsor**

Boehringer Ingelheim reserves the right to discontinue the trial overall or at a particular trial site at any time for any of the following reasons:

1. New toxicological findings or serious AEs invalidate the earlier positive benefit-risk-assessment. More specifically, the trial will be terminated if more than 50% of the subjects show drug-related and clinically relevant AEs of moderate or severe intensity, or if at least one drug-related serious AE is reported that is considered to be unacceptable.
2. The expected enrolment goals overall or at a particular trial site are not met
3. Violation of GCP, or the CTP, or the contract with BI by a trial site or investigator, disturbing the appropriate conduct of the trial
4. The sponsor decides to discontinue the further development of the investigational product.

Proprietary confidential information © 2017 Boehringer Ingelheim International GmbH or one or more of its affiliated companies

The trial site will be reimbursed for reasonable expenses incurred in case of trial termination (except in case of the third reason).

### **3.3.5 Replacement of subjects**

In case some subjects do not complete the trial, the trial clinical monitor together with the trial pharmacokineticist and the trial statistician are to decide if and how many subjects will be replaced. A replacement subject will be assigned a unique study subject number.

## **4. TREATMENTS**

### **4.1 TREATMENTS TO BE ADMINISTERED**

The film coated tablet 110 mg have been developed. The excipients used for the tablet are fumaric acid, D-mannitol, hydroxypropylcellulose, hypromellose (2208), magnesium stearate, crospovidone (type A), partially hydrolyzed polyvinyl alcohol, sucrose esters of fatty acids, titanium oxide, and polysorbate 80. The tablet formulations have been manufactured by Qualitech Pharma Co.,Ltd..

The molecular weight of DE (free base) is 627.7 g/mol. DE is administered as methanesulfonic acid salt. Dose refers to a dose of the free base. The conversion factor is 0.867; 627.7 mg of DE free base equals 723.8 mg of DE methanesulfonic acid salt. A dose of DE was calculated as a free base.

#### **4.1.1 Identity of BI investigational product and comparator product**

The characteristics of the test product are given below:

Substance: Dabigatran Etexilate (BIBR 1048)  
Pharmaceutical formulation: Tablet, film coated  
Source: Nippon Boehringer Ingelheim Co., Ltd.  
Unit strength: 110 mg  
Posology: Day 1 in Visit 2 and Visit 3: 1-0-0  
Route of administration: p.o.  
Duration of use: One day (single dose) for each treatment

The characteristics of the Non-investigational medicinal product (NIMP) / Auxiliary Medicinal Product (AMP) are given below:

Name: Pariet®  
Substance: Rabeprazol sodium  
Pharmaceutical formulation: Tablet  
Source: Eisai Co., Ltd.  
Unit strength: 20 mg  
Posology: Day -4 to Day 1 in Visit 3: 1-0-0  
Route of administration: p.o.  
Duration of use: Five days (single dose)

#### 4.1.2 Method of assigning subjects to treatment groups

After it has been determined that the subject meets all eligibility criteria, a unique subject number will be assigned. The number should be recorded on all electric CRFs and correspondence regarding the subject.

Once a subject number has been assigned, it cannot be reassigned to any other subject.

#### 4.1.3 Selection of doses in the trial

As the standard clinical dose, 75 mg and 110 mg of DE capsule are available. Between 2 dosages, 110 mg is used for this study because 110 mg b.i.d. is more common as the initial dose in elderly patients [P16-00895].

The dose of rabeprazole selected for this trial reflects higher standard clinical doses.

#### 4.1.4 Drug assignment and administration of doses for each subject

This trial is a single arm study. All subjects will receive the two treatments in a specified order: Single dose of dabigatran etexilate without (Visit 2) and with (Visit 3) rabeprazole. Rabeprazole will be administrated at 6:00 on Day -4 to Day 1 of Visit 3. The treatments to be evaluated are outlined in Table 4.1.4: 1 below.

Table 4.1.4: 1 Dosage and treatment schedule

Treatment	Substance	Formulation	Unit strength	Dosage	Total dose
Dabigatran etexilate with rabeprazole (Test)	Dabigatran etexilate and Rabeprazole sodium	Tablet	110 mg	1 tablet on Day 1 2 tablet from Day -4 to day 1 in Visit 3	110 mg 20 mg
Dabigatran etexilate without rabeprazole (Reference)	Dabigatran etexilate	Tablet	110 mg	1 tablet on Day 1	110 mg

The medications will be administered as a single oral dose together with about 200 mL of water to a subject in the sitting/standing position under supervision of the investigating physician or an authorised designee. The so-called four-eye principle (two-person rule) should be applied for administration of trial medication. Administration of medications for each Period will be performed following an overnight fast starting no later than 10 h before scheduled dosing.

Subjects will be kept under close medical surveillance until 48 h following DE administration. During the first 2 h after DE administration, they are not allowed to lie down

Proprietary confidential information © 2017 Boehringer Ingelheim International GmbH or one or more of its affiliated companies

(i.e., no declination of the upper body of more than 45 degrees from upright posture). For restrictions with regard to diet see [Section 4.2.2.2](#).

The treatments of DE will be separated by a wash-out phase of at least 4 days

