## **CLINICAL TRIAL PROTOCOL SYNOPSIS**

Name of company: Boehringer Ingelheim		Tabulated Trial Protocol		
Name of finished product: Pradaxa® (Prazaxa® in Japan)				
Name of active ingredient: Dabigatran etexilate, BIBR 1048 MS				
Protocol date: 20 Apr 2017	Trial number: 1160.270		Revision date: Not applicable	
Title of trial: Relative bioavailability of tablet formulation of dabigatran etexilate with and without co-administration of rabeprazole in healthy male subjects (an open-label, single-oral-dose, two-period, single-arm study)				
Principal Investigator: [REDACTED] Address: [REDACTED] Phone: [REDACTED] Fax: [REDACTED]				
Trial site: [REDACTED] Address: [REDACTED] Phone: [REDACTED] Fax: + [REDACTED]				
Clinical phase:	I			
Objective:	To investigate relative bioavailability of a tablet formulation of dabigatran etexilate with and without co-administration of rabeprazole in healthy male subjects			
Methodology:	Open-label, single-oral-dose, two-period, single-arm study			
No. of subjects:				
total entered:	36			
each treatment:	36			
Diagnosis:	Not applicable			
Main criteria for inclusion:	Healthy male subjects, age of 20 to 40 years, body mass index (BMI) of 18 to 25 kg/m 			
Test product:	Dabigatran etexilate tablet formulation			
dose:	110 mg single dose with and without a single dose of rabeprazole 20 mg			
mode of admin.:	Oral with 200 mL of water after an overnight fast of at least 10 hours			

Proprietary confidential information © 2017 Boehringer Ingelheim International GmbH or one or more of its affiliated companies

Name of company: Boehringer Ingelheim		Tabulated Trial Protocol				
Name of finished product: Pradaxa® (Prazaxa® in Japan)						
Name of active ingredient: Dabigatran etexilate, BIBR 1048 MS						
Protocol date: 20 Apr 2017	Trial number: 1160.270		Revision date: Not applicable			
Comparator product: Not applicable						
dose:						
mode of admin.:						
Duration of treatment: One day (single dose) for dabigatran etexilate at Visit 2 and Visit 3, and 5 days for rabeprazole at Visit 3						

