### 3. DESCRIPTION OF DESIGN AND TRIAL POPULATION

#### 3.1 OVERALL TRIAL DESIGN AND PLAN

The study will be performed as an open-label, single-oral-dose, two-period, single-arm trial in healthy male subjects in order to compare BA of DE with and without rabeprazole. The subjects will be allocated to a treatment sequence, DE without rabeprazole and then DE with rabeprazole. To make sure to increase intragastric pH, 20 mg of rabeprazole will be administrated once daily on Day -4 to -1 of Visit 3 (pre-medication). Pre-medication of rabeprazole starts at the following day of Day 3 of Visit 2. The treatments will be a single dose of 110 mg of DE with or without rabeprazole in a fasting state on Day 1 in both Visit 2 and Visit 3. For details refer to [Section 4.1](#).

[figure not shown]

Figure 3.1: 1

Trial Design

There will be a period of 6 days between administrations of DE. At least 4 days of washout are required in consideration of the period when measurable drug levels effects are still likely to be present. The interval of DE administrations satisfies this requirement.

An overview of all relevant trial activities is provided in the [Flow Chart](#). For visit schedule and details of trial procedures at selected visits, refer to [Sections 6.1](#) and [6.2](#), respectively.

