#### **4.1.6 Packaging, labelling, and re-supply**

Tablet formulation of DE and rabeprazole will be provided by NBI.

The clinical trial supply of tablet formulations and rabeprazole consists of boxes enclosing aluminium pouches in which the trial medication is packed in press through package sheets. Boxes of tablet formulations are labelled with trial identification and not with rabeprazole.

For details of packaging and the description of the label, refer to the ISF.

Examples of the labels will be available in the ISF.

The telephone number of the trial site is given in the subject information form.

No re-supply is planned.

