#### **4.1.8 Drug accountability**

The investigational drug storage manager will receive the investigational drugs delivered by the sponsor when the following requirements are fulfilled:

- Approval of the trial protocol by the IRB
- Availability of a signed and dated clinical trial contract between the sponsor and the head of the trial site
- Approval/notification of the regulatory authority, e.g., competent authority
- Availability of the curriculum vitae of the principal investigator
- Availability of a signed and dated clinical trial protocol

Only authorized personnel as documented in the form 'Trial Staff List' may dispense medication to trial subjects. The trial medication must be administered in the manner specified in the CTP. All unused medication will be disposed locally by the trial site upon written authorization by the clinical monitor. Receipt, usage and disposal must be documented on the respective forms. Account must be given for any discrepancies.

The investigational drug storage manager must maintain records of the product's delivery to the trial site, the inventory at the site, the use by each subject, and the disposal of unused products.

These records will include dates, quantities, and batch / serial numbers, expiry ('use-by') dates. The investigational drug storage manager will maintain records that document adequately that the subjects were provided the doses specified by the CTP, and that reconcile all investigational products received from the sponsor. At the time of disposal, the investigational drug storage manager must verify that all unused or partially used drug supplies have been returned by the clinical trial subject and that no remaining supplies are in the investigator's possession.

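### The rabeprazole tablet count in Table 4.1.4: 1 does not fit the listed 20 mg tablet, the 1-0-0 posology or the 20 mg dose in the same row

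*Protocol*

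**What the plan says.** Table 4.1.4: 1 sets out the Test and Reference treatments. For Test it lists one dabigatran etexilate tablet on Day 1 and, for rabeprazole, "2 tablet from Day -4 to day 1 in Visit 3". The Total dose column shows 110 mg and 20 mg for the two substances. The only unit strength legible in that row is 110 mg.

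The rest of the protocol describes rabeprazole as follows:

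- Section 4.1.1, on the non-investigational product, lists one tablet: "Unit strength: 20 mg", with "Posology: Day -4 to Day 1 in Visit 3: 1-0-0".
- Section 3.1 describes the pre-medication as "20 mg of rabeprazole will be administrated once daily on Day -4 to -1 of Visit 3 (pre-medication".
- The synopsis gives the dose as "110 mg single dose with and without a single dose of rabeprazole 20 mg", and its duration entry gives 5 days for rabeprazole at Visit 3.
- Section 4.1.3 says only that "The dose of rabeprazole selected for this trial reflects higher standard clinical doses". It gives no milligram amount and no tablet count.

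The SAP states no rabeprazole dose.

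**The concern.** Table 4.1.4: 1 defines the Test treatment, and rabeprazole is what separates Test from Reference. The tablet count there cannot be squared with the strength, the posology or the milligram dose given elsewhere, or with the 20 mg in its own row. Anyone who follows the count at each administration gives twice the rabeprazole described in the other sections.

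Section 4.1.8 says "The trial medication must be administered in the manner specified in the CTP". If that covers rabeprazole, the protocol specifies two different manners, and either count departs from one section. The same ambiguity reaches the SAP. Code C3 in Table 6.2: 1 (incorrect intake of trial medication) removes a subject from the PK set and is detected manually, so applying it to rabeprazole needs one clear statement of the intended intake.

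**Working it through.** **Inputs**

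- Tablet count: 2, Day -4 to Day 1 of Visit 3 (Table 4.1.4: 1)
- Total dose in the same row: 20 mg rabeprazole, 110 mg dabigatran etexilate (Table 4.1.4: 1)
- Rabeprazole strength and posology: 20 mg, 1-0-0 (Section 4.1.1)
- Administrations: Days -4, -3, -2, -1 and 1, so 5 (Flow Chart, Section 4.1.1, synopsis)
- Planned subjects: 36 (synopsis, Section 3.3)

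**Formula:** tablets x unit strength = dose.

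**Step 1. The table's own convention.** Dabigatran etexilate: 1 x 110 mg = 110 mg. This reproduces the stated total, so the columns are meant to multiply out per administration.

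**Step 2. Rabeprazole, count per administration.** 2 x 20 mg = 40 mg against the stated 20 mg, a factor of 40 / 20 = 2. One tablet would give 1 x 20 mg = 20 mg.

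**Step 3. Totals over five administrations.** 5 x 40 mg = 200 mg with two tablets; 5 x 20 mg = 100 mg with one. Neither is 20 mg, so the Total dose entry can only describe a single administration. The heading does not say so.

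**Step 4. Count for the whole period.** Two tablets over five administrations is 2 / 5 = 0.4 tablet each, against 1 under the 1-0-0 posology. That posology needs 5 tablets (100 mg); two tablets are 40 mg.

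**Step 5. Strength that would make the row consistent.** Per administration, 20 mg / 2 = 10 mg. If 20 mg were the five-day total, 20 / (2 x 5) = 2 mg. Neither strength is listed for the trial. The 5 and 10 mg doses in Section 1.2 are background pharmacology, and the product information cited in Section 9.1 is for 20 mg tablets.

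**Step 6. Other readings.** Applying the printed 110 mg strength to rabeprazole gives 2 x 110 mg = 220 mg. Counting one dabigatran plus one rabeprazole tablet fails because dabigatran is given only on Day 1, whereas the entry starts on Day -4.

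**Step 7. Tablets needed.** 36 x 5 x 1 = 180 or 36 x 5 x 2 = 360, before overage or replacement subjects. Section 4.1.6 says "No re-supply is planned", but the documents do not give the quantity supplied, so no shortage can be inferred.

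**The case against.** The strongest reply is that this is a one-character slip in a summary table. The count is the only entry that disagrees: the same row, Section 3.1, Section 4.1.1 and the synopsis all point to 20 mg, and a careful reader would query the cell before dosing. Section 4.3 has both drugs given in the study centre under supervision, Section 4.1.4 adds a two-person rule, and Section 4.1.8 requires records of use by each subject. On this view the matter is minor.

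Much of this stands. Double dosing has not been shown to be likely, the period-count reading is not a natural one, and accountability records should reveal how many tablets were used if they are kept for rabeprazole. But supervision and accountability compare what was given with what the protocol specifies, and here the protocol specifies two things. The plasma check in Section 4.3 does not help, because Section 5.5.3.1 assays only free and total dabigatran.

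PDF extraction may have dropped a rabeprazole entry from the unit strength column. That does not explain the mismatch: the count and the 20 mg dose are both legible, and the 20 mg strength comes from Section 4.1.1. If a 10 mg tablet had been intended, Section 4.1.1 would need changing in both strength and posology, so reconciliation would still be required.

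**Conclusion.** The contradiction is real, and nothing in either document resolves it. Read per administration, the table implies 40 mg where every stated trial dose is 20 mg: a factor of 2, or 200 mg against 100 mg over five days. It concerns the Test period only.

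The factor of 2 assumes the 20 mg tablet of Section 4.1.1 is the one used and the count is per administration. It measures the discrepancy on paper, not a demonstrated dosing error. The scheduled dosing days are not in dispute, and the sample size, ANOVA model, endpoints and confidence interval method do not depend on the entry. It should be fixed because it sits in the operative dosing schedule for the treatment under study. The documents do not establish which entry is intended, and this review does not say.

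**What to change.** Before dosing, reconcile the Dosage and Total dose entries of Table 4.1.4: 1 with Section 4.1.1, and check the result against Section 3.1 and the synopsis, so that tablet count x unit strength equals the stated dose per administration. Show the rabeprazole unit strength in the row if it is missing from the source table. State that the count is per administration, if that is meant, and label Total dose as per administration or per period. The sponsor decides which entry is intended.

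The cost is a wording correction to one table row, with no added procedure, subject or analysis.
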